7.3 Exploratory Endpoints (Efficacy)

Exploratory efficacy endpoints

- The proportion of subjects who are in clinical remission per the MMS, as applicable, over time
- The proportion of subjects who are in clinical response per the MMS, as applicable, over time
- The proportion of subjects achieving an RBS ≤ 1 over time, except at Week 8
- The proportion of subjects achieving Stool Frequency sub-score [SFS] ≤ 1 over time
- The change from baseline in the MMS at Week 2, at Week 4, and at Week 8

- Change from baseline in the Ulcerative Colitis Endoscopic Index of Severity (UCEIS) endoscopic score
- The change from baseline in the Geboes Index, Robarts Index, and Nancy Index at Week 8

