9.7.2 Endoscopy

The screening endoscopy may consist of either a flexible rectosigmoidoscopy or a colonoscopy. A colonoscopy is required during the Screening Phase only for those subjects who have not had a colonoscopy within 12 months prior to the Screening Visit. Subsequent endoscopies (rectosigmoidoscopies) will be performed at Week 8 or at the Early Termination Visit. The flexible rectosigmoidoscopy will not be repeated within 4 weeks of the previous rectosigmoidoscopy.

Images/Videos of all endoscopic procedures (flexible rectosigmoidoscopy/colonoscopy) will be captured and sent to a centralized reader for their assessment, which will be used for the calculation of the MMS. The endoscopy assessment performed by the Investigator will be used

to calculate the MMS for the determination of subjects who do not achieve at least a 20% decrease from baseline in the MMS at Week 8.

Mucosal biopsies, collected for assessment of histological disease activity (Section 9.8), will be performed during the Screening Phase and at the Week 8 Visit when the endoscopies are done. Biopsies should be taken from the most inflamed area of the rectum or rectosigmoid junction, while avoiding ulcerated mucosa. Week 8 biopsies should be taken from the same location as the baseline biopsy. Subjects who discontinue study prior to the Week 8 Visit will have the biopsies performed at the Early Termination Visit with the endoscopy.

Central reading of endoscopies will be performed throughout this study, and a detailed charter will address the standardization of endoscopic procedures, video recordings, and equipment, as well as the criteria for endoscopic assessment. For each subject, video recording of the entire endoscopic procedure will be performed. Annotation of the rectum, sigmoid and descending colon will be performed by the site endoscopist on withdrawal, using the equipment provided.

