9.7.3 Modified Mayo Score

The Mayo Score is an instrument designed to measure disease activity of UC. The Mayo Score ranges from 0 to 12 points. It consists of 4 sub-scores, each graded from 0 to 3 with higher scores indicating more severe disease (Appendix C).

A modification to the Total Mayo Score (TMS) will be implemented in this study. This MMS will be based on the stool frequency, rectal bleeding, and endoscopy sub-scores of the TMS and will exclude the Physician's Global Assessment (PGA) sub-score, since this is a global measure that is subjective in nature. The MMS ranges from 0 to 9 points. Clinical response is defined as a decrease from baseline in modified Mayo Score of at least 2 points and at least 25%, with an accompanying decrease in the RBS of at least 1 point or an absolute RBS of 0 or 1. Clinical remission is defined as an MMS of 2 points or lower, with no individual sub-score exceeding 1 point.

SFS

- RBS
- Endoscopy Sub-score

The frequency of the TMS assessment is described in Table 1 Schedule of Events.

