9.12 Study Completion

The End of Trial is defined as either the date of the last visit of the last subject to complete the study or the date of receipt of the last data point from the last subject that is required for primary, secondary, and/or exploratory analysis, as pre-specified in the protocol and/or the SAP, whichever is the later date.

Study completion for an individual subject is defined as reaching the Week 9 Follow-up Visit. Subjects not meeting this definition will be considered early termination subjects.

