13.4 Statistical Methods

The primary efficacy variable is the proportion of subjects who are in Clinical Remission at Week 8, as defined by an MMS of ≤ 2 , with individual sub-scores (SF and Endoscopy) ≤ 1 , and RBS = 0.

GED-0507-34-Levo treatment arms will be compared with placebo using the chi-squared test and using the Bonferroni-Holm method to control the false positive error rate. Corresponding confidence intervals for the risk ratios of GED-0507-34-Levo against placebo will be presented. Subjects who withdraw will be assumed not to be in remission at Week 8. The last-observation-carried-forward (LOCF) method will be used to impute MMS in the case of missing values in subjects completing the study. The above primary analysis does not adjust for the effects of center under the assumption that there will be many centers who do not recruit at least 1 subject on every treatment. Should this assumption not appear to be the case, the primary analysis methodology will be updated in the SAP prior to breaking the blind for the study.

The primary analysis of the primary efficacy variable will be on the mITT population and will be the comparison of each of the GED-0507-34-Levo doses against placebo as described above.

Additional supportive analysis of the primary efficacy variable will be performed on the ITT and PP populations. A further exploratory log-binomial regression analysis will be performed to investigate the association of prognostic factors with proportion of subjects in Clinical Remission at Week 8.

Summary statistics will be presented for efficacy variables and their changes from baseline at each time point on the mITT, ITT, and PP populations.

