13.6 Efficacy Analysis

The mITT population (Section 13.2) will be the primary population for efficacy analyses. Supportive analyses using the ITT and PP populations will also be performed for the primary efficacy endpoint.

The primary efficacy variable is the proportion of subjects achieving a clinical remission in the MMS at Week 8, defined as a MMS of ≤ 2 with individual sub-scores (SF and Endoscopy) ≤ 1 , and RBS = 0.

The methodology for the primary efficacy analysis is described in Section 13.4. The following secondary and exploratory efficacy endpoints will be analyzed using similar methodology.

- The proportion of subjects achieving clinical response at Week 8, defined as a decrease from baseline in the MMS of at least 2 points and at least 25 %, along with a reduction in the RBS of at least 1 point or an absolute RBS of ≤ 1
- The proportion of subjects achieving endoscopic remission at Week 8, defined as a Mayo endoscopic sub-score of 0
- The proportion of subjects achieving endoscopic response at Week 8, defined as a decrease from baseline of at least 1 point in the Mayo endoscopic sub-score
- The proportion of subjects achieving a RBS \leq 1 at Week 8

Additional endpoints may be added to the hierarchy and specified in the SAP.

Summary of all efficacy endpoints over time will be provided using frequency and percentage for categorical endpoints and descriptive statistics for continuous endpoints.

The MMS consists of the SFS, RBS, and endoscopy sub-scores of the TMS and excludes the PGA sub-score, since this is a global measure that is subjective in nature. Each of these parameters will be assessed on a scale of 0 to 3. The sum of scores for all 3 parameters will determine the MMS. The MMS ranges from 0 to 9 points.

Clinical response is defined as a decrease from baseline in MMS of at least 2 points and at least 25%, with an accompanying decrease in the RBS of at least 1 point or an absolute RBS of 0 or 1. Assessment of sigmoidoscopic appearance will be performed in the worst inflamed area in the rectum or in the sigmoid if the rectum is not inflamed. The same area should be evaluated at baseline and at the End of Study/Early Withdrawal Visit.

Images of all endoscopic procedures will be captured and sent to a centralized reader for their assessment.

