Improvement of symptoms at Weeks 2, 4, 6, and 8 will be assessed by using 2 individual parameters of the MMS: rectal bleeding and stool frequency. Subjects will report details regarding rectal bleeding and stool frequency to the electronic diary system every day during the study. Assessment of rectal bleeding and stool frequency will be done by the subject. The Investigator will calculate the average score of each parameter for the last 3 available days in the

5-day period immediately prior to each clinic visit and record the score in the CRF. No data older than 5 days will be used.

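### In a completer without a Week 8 endoscopy, LOCF of the Modified Mayo score can only carry a pre-treatment endoscopy, and Section 13.4 does not say which value is carried

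*Combined protocol and SAP*

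**What the plan says.** - **Score.** Section 9.7.3: "This MMS will be based on the stool frequency, rectal bleeding, and endoscopy sub-scores of the TMS". It runs from 0 to 9. Under Section 13.4, remission needs a total of at most 2, stool frequency (SFS) and endoscopy each at most 1, and rectal bleeding (RBS) of 0.
- **Missing data.** Section 13.4 has two rules. For withdrawals: "Subjects who withdraw will be assumed not to be in remission at Week 8". For completers: "The last-observation-carried-forward (LOCF) method will be used to impute MMS in the case of missing values in subjects completing the study". The second rule names neither the visit nor the component that is carried.
- **Completer.** Section 9.12: "Study completion for an individual subject is defined as reaching the Week 9 Follow-up Visit". It sets no condition on the Week 8 endoscopy.
- **Endoscopy schedule.** Section 9.7.2, after the screening procedure: "Subsequent endoscopies (rectosigmoidoscopies) will be performed at Week 8 or at the Early Termination Visit". Table 1 agrees.
- **Score schedule.** Table 1 nevertheless marks the Modified Mayo score (MMS) at every visit from screening to Week 8, and Section 7.3 lists "The change from baseline in the MMS at Week 2, at Week 4, and at Week 8". The synopsis places the score only at baseline and at Week 8 or early termination.
- **Secondary endpoints.** Section 13.6, introducing clinical response and the endoscopic endpoints: "The following secondary and exploratory efficacy endpoints will be analyzed using similar methodology".
- **SAP.** Section 13.1 refers to a separate, comprehensive SAP, which is not in the text supplied.

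**The concern.** A subject who attends Week 9 but has no usable Week 8 endoscopy has not withdrawn, so the non-remission rule does not apply and LOCF does. No on-treatment endoscopy is scheduled before Week 8, so any carried score, or carried endoscopy sub-score, rests on the screening procedure.

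Two competent programmers could classify this subject differently on the primary endpoint. One carries the entry score and records a failure. The other finds a Week 6 score in the database, as Table 1 implies, or fills in only the missing sub-score, and may record a remission or a clinical response. In the second case a pre-treatment finding stands in for the Week 8 endoscopy that the endpoint requires.

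**Working it through.** **1. The plan's own figure.** Inputs from Section 13.3: remission 6% and 26%, each multiplied by 0.85 for dropout, giving p1 = 0.051 and p2 = 0.221; one-sided alpha 0.025 after Bonferroni-Holm; power 85%. The unpooled formula is

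n = (z_alpha + z_beta)² [p1(1−p1) + p2(1−p2)] / (p2−p1)² = (1.960 + 1.036)² × 0.2206 / 0.0289 = 68.5, so 69 per arm.

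This agrees with the plan. At alpha 0.05 the same formula gives 54.9, so 55, which also agrees. Power at n = 69 is Φ(0.170 / √(0.2206/69) − 1.960) = 85.2%. The concern does not dispute the sample size.

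**2. Who is affected.** Only completers without a Week 8 endoscopy sub-score. Withdrawals have their own rule. The rule against repeating the procedure within 4 weeks does not produce such cases, because screening is always more than 4 weeks before Week 8.

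**3. What could be carried.** Three rules fit the text:
- (a) the entry MMS;
- (b) the whole Week 6 MMS, which contains Week 6 symptoms and the screening endoscopy;
- (c) the endoscopy sub-score alone, added to observed Week 8 symptoms.

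Rules (b) and (c) differ whenever symptoms change between Week 6 and Week 8.

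**4. What each rule can produce.** I listed every entry profile allowed by the eligibility ranges. Section 8.1 (SFS 1–3, RBS 1–2, endoscopy 1–3, total 4–8) gives 3 × 2 × 3 = 18, less the one profile with total 3, so 17. Section 10.2 as printed (SFS 2–3, RBS 1–2, endoscopy 2) gives 2 × 2 × 1 = 4. These are counts of score combinations, not patient frequencies.

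| | Section 8.1 (17) | Section 10.2 as printed (4) |
|---|---|---|
| Rule (a): remission / response possible | 0 / 0 | 0 / 0 |
| Rules (b), (c): remission possible | 5 | 0 |
| Rules (b), (c): clinical response possible | 17 | 4 |

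The 5 profiles are those with screening endoscopy 1. With SFS 0 or 1 and RBS 0 the imputed total is 1 or 2. Response is possible throughout because 25% of a total of 4 to 8 is 1 to 2 points, so a 2-point fall in SFS + RBS is enough once the RBS condition is met. The endoscopic endpoints cannot be met by carrying forward: a reused screening score shows no decrease and is never 0.

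**5. Expected size.** The documents give none of the following rates; all are assumptions. Among 59 completers per arm (Table 2), 2–5% lack the Week 8 endoscopy. Of these, 10–40% had screening score 1, and 10–40% have RBS 0 and SFS at most 1 at the visit whose symptoms are used.
- Low: 59 × 0.02 × 0.1 × 0.1 = 0.01 imputed remitters per arm.
- High: 59 × 0.05 × 0.4 × 0.4 = 0.47 imputed remitters per arm.

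For comparison, expected remitters are 0.051 × 69 = 3.5 on placebo and 0.221 × 69 = 15.2 on active treatment. One subject moves an arm by 1/69 = 1.4 points.

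**6. Power if these completers count as failures.** Multiply both rates by (1 − m), where m is the affected share of completers, equal across arms and unrelated to outcome:
- m = 2%: 84.4%
- m = 5%: 83.0%
- m = 10%: 80.5%
- m = 15%: 77.8%

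**The case against.** The strongest reply is that the effect is negligible and the separate SAP will settle it. Section 13 claims only to outline key elements, fewer than half a remitter per arm is at issue even at the high end, and under Section 10.2 as printed no remission can arise this way. All of that stands, and it limits the weight of the point. The gap remains, because Section 13.4 states the primary missing-data rule and, followed as written, that rule can misclassify a subject.

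Stronger readings are tempting, and the documents do not support them:
- **The 5-day limit.** Section 13.6 says "No data older than 5 days will be used", and a reader might infer that this already forbids carrying Week 6 data. It does not. The sentence tells the investigator how to average diary days before a visit. A Week 6 score built from its own window complies.
- **Response from all 17 profiles.** A reader might infer that clinical response is broadly compromised. The count shows only that symptoms alone can meet the definition in Section 7.2.1, which requires no endoscopic improvement. A reused endoscopy adds nothing to the fall. It can mislead only if the unseen endoscopy worsened enough to cancel the fall or, under rule (b), if symptoms changed after Week 6.
- **Diary gaps.** A reader might extend the objection to completers with an endoscopy but no Week 8 diary score. For them earlier on-treatment values exist, so the endoscopy problem does not arise.
- **Every imputed remission is false.** It is not. Under rule (c) it is false only if the unseen endoscopy was 2 or 3.

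**Conclusion.** The concern holds as a gap in the primary missing-data rule. For a completer without a Week 8 endoscopy, LOCF can carry only a pre-treatment endoscopy, and the rules compatible with Section 13.4 can classify that subject differently for remission and for clinical response. It should be settled before unblinding.

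The expected effect on the primary endpoint is small: 0.01 to 0.47 imputed remitters per arm on the assumed rates, not all false, and none if the endoscopy range in Section 10.2 is meant as printed. The printed signs there may have been altered when the PDF was read, so the Section 8.1 range cannot be set aside. Nothing in the documents shows that the effect would favour either arm, and the point does not call the sample size into question. The conclusion is limited to the text supplied; the SAP may already contain the rule.

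**What to change.** In Section 13.4 and the SAP, replace the LOCF sentence with:

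*The endoscopy sub-score is never carried forward. A completer without a Week 8 endoscopy sub-score is counted as not in remission and as a non-responder for clinical response and the endoscopic endpoints. LOCF, if kept, is limited to SFS and RBS from on-treatment visits when the Week 8 endoscopy is present; a sensitivity analysis counts these subjects as failures.*

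This extends the treatment Section 13.4 already gives to withdrawals. In Section 7.3 and Table 1, either state that any MMS reported at Weeks 1–6 reuses the screening endoscopy, so that its change is only the change in SFS + RBS, or report SFS and RBS alone at those visits.

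The cost is wording only, with no new procedure. The downside is a slight loss of power, to about 84.4% if 2% of completers become failures and 83.0% if 5% do, against 85.2% with none. These shares are assumptions. Compared with carrying the entry MMS there is no loss, because that rule already makes the same subjects failures.

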13.5 Background and Demographic Characteristics

Subjects' age, height, weight, and other continuous demographic and baseline characteristics will be summarized using descriptive statistics, while gender, race, and other categorical variables will be provided using frequency tabulations. Medical history data will be summarized using frequency tabulations by system organ class and preferred term.

13.5.1 Subject Disposition

Subject disposition (analysis population allocation, entered, discontinued along with primary reason for discontinuation, completed) will be summarized using frequency and percentage. Time to withdrawal from the start of study medication will be compared between the three treatment groups using Kaplan-Meier curves.

A summary of subjects enrolled by site will be provided.

Protocol violations/deviations will be summarized using frequency tabulations.

13.6 Efficacy Analysis

The mITT population (Section 13.2) will be the primary population for efficacy analyses. Supportive analyses using the ITT and PP populations will also be performed for the primary efficacy endpoint.

The primary efficacy variable is the proportion of subjects achieving a clinical remission in the MMS at Week 8, defined as a MMS of ≤ 2 with individual sub-scores (SF and Endoscopy) ≤ 1 , and RBS = 0.

The methodology for the primary efficacy analysis is described in Section 13.4. The following secondary and exploratory efficacy endpoints will be analyzed using similar methodology.

- The proportion of subjects achieving clinical response at Week 8, defined as a decrease from baseline in the MMS of at least 2 points and at least 25 %, along with a reduction in the RBS of at least 1 point or an absolute RBS of ≤ 1
- The proportion of subjects achieving endoscopic remission at Week 8, defined as a Mayo endoscopic sub-score of 0
- The proportion of subjects achieving endoscopic response at Week 8, defined as a decrease from baseline of at least 1 point in the Mayo endoscopic sub-score
- The proportion of subjects achieving a RBS \leq 1 at Week 8

Additional endpoints may be added to the hierarchy and specified in the SAP.

Summary of all efficacy endpoints over time will be provided using frequency and percentage for categorical endpoints and descriptive statistics for continuous endpoints.

The MMS consists of the SFS, RBS, and endoscopy sub-scores of the TMS and excludes the PGA sub-score, since this is a global measure that is subjective in nature. Each of these parameters will be assessed on a scale of 0 to 3. The sum of scores for all 3 parameters will determine the MMS. The MMS ranges from 0 to 9 points.

Clinical response is defined as a decrease from baseline in MMS of at least 2 points and at least 25%, with an accompanying decrease in the RBS of at least 1 point or an absolute RBS of 0 or 1. Assessment of sigmoidoscopic appearance will be performed in the worst inflamed area in the rectum or in the sigmoid if the rectum is not inflamed. The same area should be evaluated at baseline and at the End of Study/Early Withdrawal Visit.

Images of all endoscopic procedures will be captured and sent to a centralized reader for their assessment.

Improvement of symptoms at Weeks 2, 4, 6, and 8 will be assessed by using 2 individual parameters of the MMS: rectal bleeding and stool frequency. Subjects will report details regarding rectal bleeding and stool frequency to the electronic diary system every day during the study. Assessment of rectal bleeding and stool frequency will be done by the subject. The Investigator will calculate the average score of each parameter for the last 3 available days in the

5-day period immediately prior to each clinic visit and record the score in the CRF. No data older than 5 days will be used.

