7 STUDY ENDPOINTS

7.1 Primary Endpoint

The primary endpoint of this study is the proportion of subjects achieving a clinical remission in the Modified Mayo score (MMS) at Week 8, defined as an MMS of ≤ 2 , with individual subscores (stool frequency [SF] and Endoscopy) ≤ 1 and Rectal Bleeding sub-score (RBS) = 0

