13.3 Sample Size and Power Considerations

Given that the purpose of this Phase 2a trial is to determine whether the drug is efficacious and therefore whether to proceed with further development, there is only 1 outcome of interest: superiority of 1 or more experimental arms to the control. In this scenario, a one-sided testing framework is appropriate.

Moreover, given the need for the trial to be small (one or more Phase 3 trials will be required to confirm the efficacy), standard type I error rate control at the 2.5% level is not strictly necessary. For decisions concerning the future of the project, the sponsor will consider a more relaxed approach to false positive rate, allowing a 5% type I error for the one-sided test of the null hypothesis (ie, the primary outcome is no different between each treatment group and control) rather than the usual 2.5% required for a pivotal trial. The use of this higher type I error and of a low type II error of 15% give to the trial a high statistical power to detect the clinically meaningful effects while maintaining an acceptable and feasible size. Finally, because this trial is

a multiple-experimental arm randomized trial with a control, sample size is increased in order to maintain an overall type I error rate as close as possible to the nominal value of 5%. Assuming the following:

- A 6% Clinical Remission rate for the placebo, which after allowing for a 15% dropout rate being interpreted as treatment failure, equates to a 5.1% Clinical Remission rate.
- A 26% Clinical Remission rate for the highest dose of GED-0507-34-Levo (20% more than placebo group), which after allowing for a 15% dropout rate being interpreted as treatment failure, equates to a 22.1% Clinical Remission rate.
- A type I (α) error of 0.05.
- A power of 85%, type II (β) error = 0.15, to detect, if it exists, the above stated difference between GED-0507-34-Levo and placebo.
- A one-tailed test for proportions.
- A drop-out rate of 15%.

Fifty five (55) subjects per group are needed.

However, in order to take into account the multiplicity of the tests and the need of maintaining the experiment-wise error at the nominal alpha level, the number of subjects per group is increased to 69, for a total of 207 subjects. With this number of subjects, the alpha level actually considered is 2.5%, as the Bonferroni-Holm method will require for the significance testing of the lower p-value.

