Appendix C Modified Mayo Scoring System

Stool Frequency Sub-score (SFS)*

- 0 = Normal number of stools for this patient
- 1 = 1 2 stools more than normal
- 2 = 3 4 stools more than normal
- 3 = 5 or more stools more than normal
- * Each patient serves as his or her own control to establish normal stool frequency and the degree of abnormal stool frequency.

Rectal Bleeding Sub-score (RBS)**

- 0 = No blood seen
- 1 = Streaks of blood with stool less than half the time
- 2 = Obvious blood with stool most of the time
- 3 = Blood alone passed
- ** The daily bleeding score represents the most severe bleeding of the day.

Endoscopy sub-score: Findings of flexible sigmoidoscopy

- 0 = Normal or inactive disease
- 1 = Mild disease (erythema, decreased vascular pattern)
- 2 = Moderate disease (marked erythema, absent vascular pattern, friability, erosions)
- 3 = Severe disease (spontaneous bleeding, ulceration)

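### Section 13.6 scores Week 8 stool frequency and bleeding from the days just before the endoscopy visit and excludes no bowel-preparation or endoscopy days, so a true remitter can be scored as a non-remitter

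*Combined protocol and SAP*

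**What the plan says.** Section 13.6 sets the scoring rule for the two diary items. It begins "The Investigator will calculate the average score of each parameter for the last 3 available days in the" and continues "5-day period immediately prior to each clinic visit and record the score in the CRF". It then adds: "No data older than 5 days will be used". Sections 9.7.1 and 13.6 expect a diary entry every day.

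On the procedure, Section 9.7.2 states: "Subsequent endoscopies (rectosigmoidoscopies) will be performed at Week 8 or at the Early Termination Visit". The same section requires a video clip covering rectum, sigmoid and descending colon. Table 1 lists endoscopy and biopsies only at Screening and at Visit 7, so Week 8 is the only scheduled on-treatment visit with an endoscopy.

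Section 7.1 defines remission as an MMS of at most 2, with stool frequency and endoscopy sub-scores of at most 1 "and Rectal Bleeding sub-score (RBS) = 0". In Appendix C the top stool grade is "3 = 5 or more stools more than normal", and for bleeding "The daily bleeding score represents the most severe bleeding of the day".

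No section mentions bowel preparation, excludes a preparation or endoscopy day, defines an available day, or says whether the three-day mean is rounded to a whole grade.

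**The concern.** The rule always reaches first for the days nearest the visit. At Week 8 those are the days most likely to carry the effect of preparing for an endoscopy, because a recording up to the splenic flexure makes some preparation plausible. A stool count raised by preparation is not a symptom of colitis, yet it enters the stool frequency sub-score and the MMS.

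This falls on the primary time point and on no other scheduled on-treatment visit. At stake are the Week 8 remission rate in each arm, and with it the absolute difference and the power. Clinical response at Week 8 also uses the diary scores.

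**Working it through.** **Which days are exposed.** The window lies before the visit. Counting back, the day before is day −1. With complete entries, days −1, −2 and −3 are scored. An entered preparation day at −1 is therefore always scored. An endoscopy day is scored only if the procedure is done before the visit date and falls among the last three entered days. Preparation or a procedure on the visit day itself is already outside the window.

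**Effect on the stool frequency sub-score (limit 1).** Days are listed oldest first, with the last day affected.
- 1, 1, 1 gives 3/3 = 1.00: passes. This is the unaffected case.
- 1, 1, 3 gives 5/3 = 1.67: fails, and still fails if rounded to 2.
- 0, 1, 3 and 1, 1, 2 each give 4/3 = 1.33: fail unrounded, pass if rounded to 1. With endoscopy 1, the unrounded MMS is 2.33, also above 2.
- 0, 0, 3 gives 3/3 = 1.00: passes. With endoscopy 1 and bleeding 0, the MMS is 2.00 and the subject is still in remission.

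**Effect on the bleeding sub-score (must be 0).** This applies only if biopsies are taken before the visit date.
- 0, 0, 1 gives 0.33: fails unrounded, passes if rounded.
- 0, 0, 2 gives 0.67: fails either way.

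**The plan's own power.** Section 13.3 gives 6% × 0.85 = 5.1% for placebo ("equates to a 5.1% Clinical Remission rate"), 26% × 0.85 = 22.1% for the highest dose, 69 per arm, and one-sided 2.5% for the first Holm step. With unpooled variance:

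n = (z₁₋α + z₁₋β)² [p₁(1−p₁) + p₂(1−p₂)] / (p₂−p₁)²

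The variance term is 0.051 × 0.949 + 0.221 × 0.779 = 0.2206.
- α = 5%: (1.645 + 1.036)² × 0.2206 / 0.17² = 54.9, so 55 per arm, as stated.
- α = 2.5%: (1.960 + 1.036)² × 0.2206 / 0.17² = 68.5, so 69 per arm, as stated.
- Power at 69: Φ(0.17 / √(0.2206/69) − 1.960) = Φ(1.047) = 85.2%. The plan says 85%.

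**Sensitivity.** Let m be the share of true remitters in every arm scored as non-remitters for this reason. The documents give no value for m. Both rates are multiplied by (1 − m):
- m = 5%: 4.8% v 21.0%, power 83.0%; 73 per arm would restore 85%.
- m = 10%: 4.6% v 19.9%, power 80.5%; 78 per arm.
- m = 20%: 4.1% v 17.7%, power 74.8%; 90 per arm.

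A pooled-variance calculation starts lower, at about 84%, and gives about 81%, 79% and 73%. The falls are of similar size.

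**The case against.** The strongest reply is that the exposure may be small or absent. The documents describe no preparation, and the Week 8 procedure is a rectosigmoidoscopy, not a colonoscopy. Preparation might be done only on the morning of the visit, outside the window. This stands: the omission is certain, its frequency is not.

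The assumed losses have no source in the documents. If the planned 6% and 26% come from trials that also did endoscopy at the assessment, part of the loss may already be in them. This stands too, so the power figures are illustrative only.

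Section 13.1 refers to a separate comprehensive SAP, and Section 9.7.2 to an endoscopy charter. Either might cover the point, and neither is in the text reviewed. The scoring rule itself, however, is written in full in Section 13.6 without an exception.

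A reader might also infer more than the text supports:
- **That biopsy bleeding routinely spoils the Week 8 bleeding score.** Biopsies taken on the visit day come after the window closes. The mechanism needs an endoscopy before the visit date.
- **That entry scores are inflated in the same way.** Table 1 puts the screening endoscopy at Weeks −4 to −1 and Baseline at Day 1, so on that schedule it lies outside the 5-day Baseline window.
- **That the 5-day limit leaves nothing to replace an affected day.** Three of five days are used. Excluding one still leaves up to four.

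**Conclusion.** The rule as written scores an entered preparation day on the eve of the Week 8 visit and can turn a true remitter into a non-remitter. It does not do so in every pattern: 1, 1, 3 fails under any rounding, 0, 0, 3 passes, and several patterns depend on a rounding rule that the plan omits.

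The conclusion rests on the assumption that preparation falls on the day before the visit or that the endoscopy precedes the visit date. The size cannot be fixed from the documents. A loss of 5% to 20% of true remitters would cost roughly 2 to 10 points of power.

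It might be read as a bias towards the drug. The documents do not support that: with blinded arms and the same procedure in each, the misclassification should be similar across arms. The harm is lower remission rates, a smaller absolute difference and less power. The change is worth making because it is cheap and concerns the primary endpoint.

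**What to change.** In Section 13.6:
- State that diary days with bowel preparation or endoscopy, and any day between the procedure and the visit, are not used.
- Score the last three remaining days in the 5-day window. Only if fewer than three remain, count the 5-day window back from the start of preparation. Amend the bar on older data to allow this one exception.
- State at the same time whether the three-day mean is rounded before the cut-offs are applied.

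In the eCRF, record the preparation and procedure dates. They are hard to recover reliably afterwards if they were never collected, so this belongs before data collection.

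The cost is a sentence or two and one or two eCRF dates. The downside is that the scored days are slightly older. With complete entries, preparation at day −1 moves them from −1 to −3 to −2 to −4, one day older. Preparation at −2 with endoscopy at −1 moves them to −3 to −5, two days older and still inside the window.
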